11. Safety Assessment	34
11.1. Definition.....	34
11.2. Adverse Event Collection and Reporting.....	35
11.3. Suspected Unexpected Serious Adverse Reaction (SUSAR) Report.....	36
12. Monitoring	37
12.1. Installation of Data and Safety Monitoring Board (DSMB)	37

Confidential

MDR-END v14.0, 20Mar2020

12.2.	Monitoring Plans	37
13.	Ethical Considerations of the Study.....	38
13.1.	Compliance of Study Ethical Regulations	38
13.2.	Obtaining written informed consent from Subjects	39
13.3.	Protection of Personal Records.....	40
13.4.	Compensation and Indemnities Provided to Subjects.....	40
14.	Administrative Requirements	41
14.1.	Change of Study Protocols	41
14.2.	Subject identification log and screening/enrollment log.....	41
14.3.	Completing Case Report Forms (CRF).....	41
14.4.	Quality Assurance of Data	41
14.5.	Storage of Records.....	42
14.6.	Completion and Stopping the Study	42
15.	References	43

Confidential

MDR-END v14.0, 20Mar2020

Summary of Research Plans

1. Background

Tuberculosis, and especially drug-resistant tuberculosis, is a huge threat to public health not only in Korea, but throughout the world. Treatment of multidrug-resistant tuberculosis (MDR-TB), which exhibits resistance to the two most powerful drugs, must use second-line anti-TB drugs. However, usage of the conventional second-line anti-TB drugs not only has low success rates, but is also accompanied by a range of issues such as side effects due to prolonged use of drugs for about two years for treatment, low compliance, and high costs. Therefore, by developing new treatment regimens for MDR-TB treatment including recently introduced new drugs to improve the treatment efficacy and shortening the therapy period, it will be possible to increase treatment compliance, and consequently raise the treatment success rate.

2. Purpose

This clinical trial is to compare the efficacy of a ‘new treatment regimen including delamanid, linezolid, levofloxacin, and pyrazinamide for nine or twelve months (investigational arm)’ and ‘the standard treatment regimen including injectables for 20 to 24 months (control arm)’ for treating fluoroquinolone sensitive multidrug-resistant tuberculosis.

3. Design of the Study

Multicenter, randomized, open-label, two arms, phase II/III clinical trial

① Group 1 (Control arm)

Minimum 20 months treatment according to the 2014 Korean guidelines for the treatment of tuberculosis and 2014 World Health Organization (WHO) guidelines

② Group 2 (Investigational arm)

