5.1.2. Multicenter, randomized, open-label, two arms, phase II/III clinical trial

- Once eligibility is confirmed and the subject consents for participation, he/she will be randomly assigned to the following two groups at 1:1.

① Group 1 (Control arm)

Treatment will be according to the 2014 Korean guidelines for the treatment of tuberculosis (19) and 2014 WHO guidelines (20). Treatment principles are summarized as follows.

- Combination of treatment regimen
 - Intensive phase regimen comprising four effective second-line anti-TB drugs (including an injectable) and pyrazinamide.
 - It is recommended that at least five active drugs be used, selected appropriately based on drug susceptibility testing (DST) results.
 - Example of regimen: pyrazinamide, a fluoroquinolone, cycloserine, prothionamide, and an injectable
 - Efforts should always be made to use a fluoroquinolone, preferentially use levofloxacin or moxifloxacin.
 - Cycloserine should be used preferentially, but when it is not possible para-aminosalicylic acid (PAS) could be used.
 - The medication like linezolid, delamanid, or bedaquiline can be added from the beginning of the treatment if the patient has a resistance to injectables. In addition, linezolid, delamanid, or bedaquiline can be used to fortify the regimen when the adverse drug reactions occur to other anti-TB drugs.
 - The usage and dosage follow 2014 Korean guidelines for the treatment of tuberculosis published by the Committee for the Revision of Korean Guidelines for Tuberculosis and the Korea Centers for Disease Control and Prevention (19) but not limited to it.

Type of Drug	Dose		
	Usual dose	Maximal dose	Usage
Ethambutol	15-20mg/kg	1600mg	Once, before or after

Confidential

MDR-END v14.0, 20Mar2020

			meal
Kanamycin Amikacin Streptomycin Capreomycin	15mg/kg, < 50 years 10mg/kg, ≥ 50 years	1000mg, < 50 years 750mg, ≥ 50 years	Once
Cycloserine	500mg, < 50 kg 750mg, 50-70 kg 750-1000mg, >70 kg	1000mg	Once or divide in two, before or after meal (best to take on an empty stomach)
Prothionamide	500mg, < 50 kg 750mg, 50-70 kg 750-1000mg, >70 kg	1000mg	Once or divide in two, after meal
PAS	150mg/kg	12g	Divide in two or three after meal

- Treatment duration

- Intensive phase is recommended to be a minimum of 8 months.
- Total treatment duration is recommended to be 20 to 24 months.

② Group 2 (Investigational Group)

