8.4. Study Visits

- Subjects will visit for study at 1 week, 2 weeks and 4 weeks after enrollment, and then every four weeks until 12 months(52 weeks), afterwards every 2 months until the end of treatment (EOT). The time of EOT is 40 or 52 weeks for the Investigational arm and will be determined individually for control arm according to the standard of care treatment.
- Subjects in the investigational arm will visit every 2 months after EOT even if it is before 12 months(52 weeks).

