10.2. Statistical Analysis Method

1) Analysis Group Definition

Data obtained from subjects through clinical trials will be analyzed by mITT (Modified Intention-To-Treatment) analysis and PP (Per-Protocol) analysis. Efficacy evaluation will be based on a mITT (Modified Intention-To-Treatment) and additional analysis on PP (Per-Protocol) group. Safety analysis will be performed on the safety group.

- The mITT (Modified Intention-To-Treatment) group includes participants who are randomized after satisfying eligibility criteria and receive study drugs at least one time.
- The PP (Per-Protocol) group includes participants that satisfy the following among mITT group.
 - 1) When completing over 80% of the planned treatment (in other words, for control arm, 64 weeks or longer treatment; For investigational arm, 32 weeks or longer treatment in the 9-month treatment group and 42 weeks or longer treatment in the 12-month treatment group)
 - 2) Participants who completed the study per protocol during the clinical trial period.
- The Safety analysis group includes participants who receive study drugs at least one time.

2) Handling of Missing Data

When categorized as 'loss to follow-up', 'withdrawal', or 'withdrawal of consent', it is deemed as following.

- ① 'Treatment failure' in the case of dropping out due to 'loss to follow-up', 'investigator's decision', 'withdrawal of consent', 'treatment failure', or 'death' during the treatment
- ② 'Not accessible' in the case of dropping out due to pregnancy during the treatment
- ③ 'Treatment failure' in the case of dropping out due to 'relapse' after the treatment completion
- ④ 'Not accessible' when there is no evidence of treatment failure, such as bacteria reversion in the case of withdrawal due to 'loss to follow-up', 'investigator's decision', 'withdrawal of consent', 'pregnancy', or 'death' after the treatment completion

3) Basic Characteristics Analysis of Subjects Prior to Administration of Study Drugs

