3.1 General Principle of Result Analysis

Data obtained from subjects through clinical trial will be analyzed by mITT (modified Intention-To-Treatment) analysis and PP (Per-Protocol) analysis. Efficacy evaluation will be based on a mITT (modified Intention-To-Treatment) and additional analysis on PP (Per-Protocol) group. Safety analysis will be performed on mITT, PP and the safety group (study drug administration group).

Subject Group	Definition
mITT	
- The mITT group includes participants who are randomized after satisfying eligibility criteria and receive study drugs at least one time. The subjects are not confirmed to be additionally resistant to fluoroquinolone, mono-resistant to rifampicin, or susceptible to rifampicin.

PP	
The PP (Per-Protocol) group includes participants that satisfy the following among the mITT group.
 
When completing over 80% of the planned treatment
 
: For control arm, 64 weeks or longer treatment; For investigational arm, 32 weeks or longer treatment in the 9-month treatment group and 42 weeks or longer treatment in the 12-month treatment group

Safety	
Participants who completed the study per protocol during the clinical trial period
 
: More than 80% of the planned period before treatment is completed, the following cases are considered protocol violation and excluded from the analysis group
 
① withdrawal or death.② The sputum test before culture conversion was not conducted③ Administration of study drug in the control arm 
The Safety analysis group includes participants who have taken study drugs at least one time.
 
: Evaluation based on the administration of study drug (delamanid or linezolid)

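### The control arm's 64-week per-protocol threshold is 80% of 80 weeks but about 74% of the stated 20-month minimum, so the 80% rule is not applied equally to the two arms

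*Combined protocol and SAP*

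**What the plan says.** The first PP criterion in Protocol 10.2 is "When completing over 80% of the planned treatment". The same sentence turns it into weeks: "for control arm, 64 weeks or longer treatment", then "32 weeks or longer treatment in the 9-month treatment group" and "42 weeks or longer treatment in the 12-month treatment group". SAP 3.1 repeats the control figure: "For control arm, 64 weeks or longer treatment".

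The planned control duration appears in several places:

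- Summary of Research Plans, section 3: "Minimum 20 months treatment according to the 2014 Korean guidelines".
- Protocol 5.1.2, control arm: "Total treatment duration is recommended to be 20 to 24 months".
- Protocol 7.1, control visit schedule: the end-of-treatment column starts at week 80.
- Protocol 8.4: the end of treatment "will be determined individually for control arm according to the standard of care treatment".

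For the investigational arm, Protocol 5.1.2 equates 9 months with 40 weeks and 12 months with 52 weeks. Protocol 8.4 uses 12 months = 52 weeks again when setting visits for both arms.

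PP is an additional analysis in Protocol 10.2 and auxiliary to mITT in SAP section 5. SAP Table 15 shows the same one-sided non-inferiority limit for both sets.

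**The concern.** A completion rule written as a percentage should ask the same of each arm. Here the control weeks appear to rest on a four-week month (20 months as 80 weeks), while the investigational weeks rest on 4.33 to 4.44 weeks per month. Measured against the stated 20-month minimum, control is then held to a looser standard.

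At stake is who enters the PP set. A control who stops at 74% of a 20-month course meets the duration criterion. An investigational participant who stops at 74% of a 40- or 52-week course (about 29.5 or 38.4 weeks) does not. Under the missing-data rule (Protocol 10.2, SAP 3.2), most on-treatment dropouts, including loss to follow-up, withdrawal of consent and death, count as treatment failures. Retaining such controls would lower control success in the analysis that supports the mITT result.

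**Working it through.** **1. Reproduce the plan's figures.** Threshold = 0.80 × printed weeks.

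- Control (week 80, Protocol 7.1): 0.80 × 80 = 64.0.
- 9-month group (40 weeks, Protocol 5.1.2): 0.80 × 40 = 32.0.
- 12-month group (52 weeks, Protocol 5.1.2): 0.80 × 52 = 41.6, rounded up to 42.

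All three reproduce, so the multiplication is right. The question is the 80.

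**2. Compare 80 weeks with 20 months**, at the protocol's 52/12 = 4.333 weeks per month.

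- 80 / 4.333 = 18.5 months.
- 20 months = 86.7 weeks; 80% of that is 69.3 weeks; 64 / 86.7 = 73.8%.
- 24 months = 104 weeks; 80% of that is 83.2 weeks; 64 / 104 = 61.5%.
- Investigational, on printed weeks: 32 / 40 = 80.0% and 42 / 52 = 80.8%.

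**3. Apply one conversion to both arms**, to see whether the gap depends on the choice.

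| Weeks per month | Control, 64 weeks of 20 months | 32 weeks of 9 months | 42 weeks of 12 months |
|---|---|---|---|
| 52/12 | 64/86.7 = 73.8% | 32/39 = 82.1% | 42/52 = 80.8% |
| 4 | 64/80 = 80.0% | 32/36 = 88.9% | 42/48 = 87.5% |
| 40/9 | 64/88.9 = 72.0% | 32/40 = 80.0% | 42/53.3 = 78.8% |

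Control is about 7 to 9 percentage points more lenient in every row. The arms agree at about 80% only when the conversions are mixed.

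**4. How many controls could be affected?** The documents give no count, so this is an illustration. Assume 48 evaluable controls (Protocol 10.1) and stopping spread evenly over 86.7 weeks. The window from 64 to 69.3 weeks holds 5.33 / 86.7 = 6.15% of those who stop.

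- 5% stop (the loss to follow-up in Protocol 10.1): 48 × 0.05 × 0.0615 = 0.15 controls.
- 20% stop (all non-success at the assumed 80% control rate): 48 × 0.20 × 0.0615 = 0.59.
- 39.0% stop (the highest historical rate printed in Protocol 2.1; the counts beside it, 342 of 1,175, give 29.1%, so this is a high value): 48 × 0.39 × 0.0615 = 1.15.

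**5. Effect of each one, if kept as a failure.** Adding one failure to 48 controls at 80% gives 38.4 / 49 = 78.4%, a fall of 1.6 points. With 45 controls at 90%, an assumption not found in the documents, it is 40.5 / 46 = 88.0%, a fall of 2.0 points. The range is therefore from 0.15 × 1.6 = 0.2 to 1.15 × 2.0 = 2.3 points, and about 1 point in the middle case, against a 10-point margin.

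**6. Controls planned for 24 months.** Their window is wider, 64 to 83.2 weeks, or 19.2 / 104 = 18.5% of the course. If every control were planned for 24 months, the counts in step 4 would be 0.4, 1.8 and 3.5. The plan states no denominator for these participants.

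**The case against.** The sponsor can fairly answer that all three thresholds are exactly 80% (after rounding up) of week counts printed in the protocol, and that week 80 is the nominal control plan just as weeks 40 and 52 are for the investigational groups. That stands as an explanation of where 64 comes from. It does not remove the conflict, because 80 weeks falls short of the protocol's own stated minimum. A reader might infer that 64 is an arithmetic slip; it is not.

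A reader might also infer that the PP result is biased toward non-inferiority. The documents do not establish that, for two reasons:

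- **Retention is uncertain.** The second PP criterion in Protocol 10.2 requires completing the study per protocol, which on a plain reading removes a control who drops out at week 66 whatever the threshold. SAP 3.1 lists withdrawal or death as a ground for exclusion, in wording that is unclear in the text available. SAP Table 1 confines that exclusion to people below 80% of the planned period, which suggests that later dropouts stay in. Retention is possible, not settled.
- **The direction can reverse.** Control duration is a recommendation and its end is set individually. A control judged to have completed treatment between 64 and 69 weeks would be kept as a success, which raises control success.

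Finally, PP is auxiliary, and the threshold has no bearing on the mITT set or the sample size.

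**Conclusion.** The inconsistency is real and internal to the documents. Sixty-four weeks is 80% of 80 weeks, but about 74% of the stated 20-month minimum and about 62% of 24 months, against 80.0% and 80.8% of the printed investigational weeks. With any single month-to-week conversion tried, the control standard is about 7 to 9 points looser.

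The consequence is limited. On a 20-month plan, the illustration gives about one affected control or fewer, and a shift in PP control success of roughly 0.2 to 2.3 points if all of them were kept as failures. This rests on evenly spread stopping and on the assumed stopping rates; the true count may be zero. It would be larger if many controls were planned for longer than 20 months. The net direction is not established, and the primary mITT conclusion is not in question. The point is worth correcting because it fixes a stated inclusion threshold at little cost.

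**What to change.** Reconcile three items: the 20-month minimum (Summary section 3, Protocol 5.1.2), the week-80 start of the end-of-treatment column (Protocol 7.1), and the 64-week threshold (Protocol 10.2, SAP 3.1). Which control duration is intended is for the sponsor to state.

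Then restate the control criterion in Protocol 10.2 and SAP 3.1 as at least 80% of planned duration, using one month-to-week conversion for both arms. If the 20-month minimum stands, the analysis cut-off becomes about 70 weeks (69.3 rounded up). That alone is not enough for longer plans: 70 / 104 is only 67% of 24 months. So state the denominator for controls planned beyond 20 months. In the same edit, make SAP 3.1 and SAP Table 1 agree on whether someone who withdraws or dies on treatment after the threshold remains in PP.

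The cost is a wording change in two documents and a possibly slightly smaller control PP set.

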7.2. Investigational arm

	Screening	Baseline Visit ¹	Treatment					End of Treatment ⁷	Treatment completion to End of Study
Weeks (w)	-2w ~ 0d n-a	0 n-a	1w	2w	4w	8w	12w ~ (Every 4w)	40w ~ 52w	~ 24month (Every 2month) ±2w
			±4d	±4d	±1w	±2w	±2w	±2w	
Consent	O								
Randomization		O							
Medical history	O								
Physical Exam	O		O	O	O	O	O	O ⁷	
Neurologic exam	O		O	O	O	O	O	O ⁷	
Sputum AFB smear	O ⁵	O ⁵	O	O	O	O	O	O	O
TB culture (solid)	O ⁵	O ⁵	O	O	O	O	O	O	O
TB culture (liquid)	O ⁵	O ⁵	O	O	O	O	O	O	O
Genotypic DST	If available								
Phenotypic DST ²	With first/reverted cultured M.TB								
LZD, Delamanid resistance examination	If needed (please see the protocol section 9.0)								
Chest X-ray (CXR)	O ⁵	O ⁵	O ⁸	O ⁸	O	O	O	O	O
Chemistry, Electrolyte	O ⁵	O ⁵	O	O	O	O	O	O ⁷	
Complete blood count	O ⁵	O ⁵	O	O	O	O	O	O ⁷	
ECG	O ⁵	O ⁵	O	O	O	O	O	O ⁷	
Urine HCG ³	O	O	O	O	O	O	O	O ⁷	
HIV, HBV ⁴		O ⁵							
Optic test	O	O	O	O	O	O	O	O ⁷	
Compliance of drug intake			O	O	O	O	O	O ⁷	
Adverse drug reaction			O	O	O	O	O	O ⁷	
Other medication ⁶	O	O	O	O	O	O	O	O ⁷	

¹Administration of anti-TB regimen can begin at baseline visit since drug-resistant TB must be treated immediately.

²Drug susceptibility test for isoniazid, rifampicin, ethambutol, pyrazinamide, streptomycin, kanamycin, amikacin, capreomycin, ofloxacin, levofloxacin, moxifloxacin, prothionamide, cycloserine, and para-aminosalicylic acid (omit for patients with results provided already).

³Only for childbearing age (the blood HCG test result can be extracted).

⁴Study drugs can be administered before the obtaining of results since eligibility is not determined by these results.

⁵Could be skipped if previous tests except ECG were been done within four weeks. In case of ECG, within 1week.

⁶Check prohibited drugs for exclusion criteria at screening visit, and check immunosuppressants including steroids after enrollment.

⁷End of treatment visit will be determined by the time of culture conversion. Omit test after end of treatment (EOT) visit.

⁸Could be skipped if previous CXR test was performed within 2 weeks

Confidential

MDR-END v14.0, 20Mar2020

8. Screening and Procedures

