8.4.2. Follow-up visits after EOT (Investigational arm only)

- Sputum AFB smear microscopy and MTB culture on liquid and solid media
- CXR

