10.1. Sample size justification

The hypothesis of this study is that the treatment success rate at 24 months after the initiation of treatment for MDR TB using the new regimen including new anti-TB drugs will not be inferior to conventional treatment regimens. (Non-inferiority test)

Presumptions when calculating sample size are as follows.

- 1) Level of significance, $\alpha = 0.025$ (one-sided test)
- 2) Type 2 error (β) set at 0.20 to maintain 80% for power of the test
- 3) Subject no. ratio (control arm : investigational arm) = 1 : 1
- 4) Primary outcome: treatment success rate at 24 months after the initiation of treatment
- 5) The hypothesis of the study is as follows.
 - ① Null hypothesis: Four drug regimen treatment success rates at 24 month are inferior to conventional treatment outcomes. ($H_0 : P_T - P_C \leq \delta$)
 - ② Alternative hypothesis: Four drug regimen treatment success rates at 24 month are not inferior to conventional treatment outcomes. ($H_1 : P_T - P_C > \delta$)

Based on the study result of Kwak et al, 'Changes in treatment outcomes of multidrug-resistant tuberculosis, Int J Tuberc Lung Dis 19(5):525-530'(3), presuming 24 month treatment success rate of control arm as 80% and 24 month treatment success rate of investigational arm as 90%, the non-inferiority margin (δ) is -0.10 which is regarded as non-inferior when the difference is less than 10% between the two arms. The number of study subjects is 48 per arm.

In addition, reflecting 1) proportion of fluoroquinolone-susceptible MDR-TB among participants with positive Xpert MTB/RIF assay of 50%, and 2) anticipating 5% lost to follow-up, the final number of participants is calculated as $N/(0.50*0.95)$ resulting in 102 persons per arm, 204 in total.

If a participant withdrew for any reasons within two weeks after enrollment, the participant will be replaced. Considering the number of replaced participants, the enrollment accrual ceiling is 220 persons maximum.

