- In order to test whether there is a statistical difference in sputum culture conversion proportion at two months of treatment between the control arm and the investigational arm (liquid and solid culture media), each arm is summarized by conversion frequency and proportion, and the sputum culture conversion proportions at two months between the two arms are compared using the Chi-square test and Fisher's exact test.

- **Sputum culture conversion proportion at six months of treatment (liquid and solid culture media)**

- In order to test whether there is a statistical difference in sputum culture conversion proportion at six months of treatment between the control arm and the investigational arm (liquid and solid culture media), each arm is summarized by conversion frequency and proportion, and the sputum culture conversion proportions at six months between the two arms are compared using the Chi-square test and Fisher's exact test.

Confidential

MDR-END v14.0, 20Mar2020

- **Proportion of treatment success at the end of treatment**

-Summarize the frequency and proportion of treatment success at the end of treatment in the investigational arm.

- **Proportion of relapse after treatment success**

-Summarize the frequency and proportion of relapse after treatment success in the investigational arm.

- **Proportion of deaths and time-to-death**

-Summarize the frequency and proportion of death in the investigational arm, and estimate median survival time using the Kaplan-Meier method.

- **Primary outcome evaluation between treatment groups according to pyrazinamide resistance**

-Presentation of treatment success rate in the control arm and the investigational arm in small groups according to the presence or absence of pyrazinamide resistance, and verification of non-inferiority of treatment success rate difference between the treatment groups

5) Safety Evaluation

Safety evaluation is performed using adverse events that occur during the clinical trial period. Summarize all adverse events and serious adverse events, adverse event frequency and percentage, and 95% confidence interval on it. Also, summarize and evaluate the occurrence rate of adverse events in relationship to the study drug and severity. The incidence of adverse events (CTCAE Grade 3 and above toxicity) between the two arms are compared using the Chi-square test or Fisher's exact test.

11. Safety Assessment

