3.7 Safety Analysis

The safety analysis evaluates subjects enrolled in this clinical trial and administered the study drug at least one time.

1) Adverse Events

- The analysis obtains the 95% confidence interval of the proportion of the subjects who have experienced one or more adverse event within each arm and performs the Chi-Square Test or Fisher's Exact Test to compare the treatment groups.
- It compares the occurrence rate of adverse drug reactions of the two arms using the Chi-square test or Fisher's exact test.
- It summarizes the number of adverse events of each arm.
- It summaries the number of expressions of five items (seriousness, severity, relation, action taken, and outcome) for each arm.
- The classification of adverse events by body system is organized according to the SOC (System Organ Class) and PT (Preferred Term) of MedDRA system.
- It describes the details such as demographic information, event date, end date, severity, relation, action taken, and outcome for the subjects who reveal serious adverse events.

2) Physical/Neurological Examination Result

- For the results of the physical/neurological examination, the analysis presents the proportion of subjects who were normal in screening visit (Visit1) and changed to abnormal at the final visit.

3) Chemistry/Electrolyte/Complete Blood Count Result

- The analysis presents the proportion of subjects who showed the chemistry/electrolyte/complete blood count result of "Normal" or "Abnormal NCS" at the baseline visit (Visit2) and changed to "Abnormal CS" at the final visit.

4) Concomitant Medication

- The analysis classifies the concomitant medication using the ATC (Anatomical Therapeutic Chemical)

Code presents it for each arm.

4. Subjects

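### Grade 3+ adverse events are compared as crude proportions over the trial period, but scheduled adverse-event checks end at end of treatment: week 40 or 52 in the investigational arm, week 80 or later in control

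*Combined protocol and SAP*

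**What the plan says.** Grade 3 and higher adverse events are a listed secondary outcome (protocol 5.3). For the analysis, protocol 10.2 says: "Safety evaluation is performed using adverse events that occur during the clinical trial period". The arms are then compared by a chi-square or Fisher's exact test: "The incidence of adverse events (CTCAE Grade 3 and above toxicity) between the two arms are compared using the Chi-square test". SAP 3.7 takes the proportion of participants with at least one event and "performs the Chi-Square Test or Fisher's Exact Test to compare the treatment groups". SAP Table 23 carries a p-value for grade 3–5 events. Neither document plans a rate per person-time, a time-to-first-event analysis or a common observation window for adverse events.

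The schedules set when participants are asked:

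- **Investigational arm (protocol 7.2).** The adverse-drug-reaction row is marked from week 1 to EOT at week 40 or 52 and is blank afterwards. Its footnote says: "Omit test after end of treatment (EOT) visit". Section 8.4.2 lists only sputum tests and chest X-ray for the two-monthly visits from EOT to month 24.
- **Control arm (protocol 7.1).** The same row is marked up to the EOT column, which begins at week 80, and is blank at the month-24 end-of-study visit. Section 5.1.2 recommends 20 to 24 months of treatment.

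Protocol 11.2 gives a start but no end for collecting adverse events. It requires serious adverse events to be reported throughout the study, in both arms.

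**The concern.** The analysis window is nominally the same 24 months in both arms, but the time during which events are looked for is not. Blood counts, chemistry, neurological examination and colour-vision testing also stop at EOT in the investigational arm. Section 11.1 counts abnormal test results as adverse events, so those go unsought as well.

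A reader of Table 23 would take it as a 24-month comparison. It is neither that nor a comparison over equal time. Side effects are part of the rationale for the new regimen (protocol 1.2 and 2.1), so a lower crude proportion in the investigational arm would probably be read as better tolerability. Conversely, a higher event rate on the short regimen could be hidden by its shorter observation.

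**Working it through.** **The plan's own figure.** The documents give none for the adverse-event comparison. The 48 per arm used below is the evaluable number for the primary outcome (protocol 10.1: success 80% and 90%, margin −0.10, one-sided 0.025, power 80%). Check: (0.80×0.20 + 0.90×0.10) × (1.960 + 0.842)² / 0.20² = 49.06, so 50 per arm. The stated 48 gives 79.1% power and is close enough. Inflation: 48/(0.50×0.95) = 101.05, given as 102.

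**Unscheduled time, taking 24 months as 104 weeks.**
- Investigational: 104 − 52 = 52 weeks, or 104 − 40 = 64 weeks.
- Control: 104 − 80 = 24 weeks, down to 0 if treatment runs to month 24.
- Scheduled checks therefore end 80 − 52 = 28 to 104 − 40 = 64 weeks earlier in the investigational arm.

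**What the crude test does at equal event rates.** Assumptions: the same hazard in both arms, events captured only to EOT, 30% with a grade 3+ event by week 40, and control observed to week 80. The cumulative hazard at week 40 is −ln(0.70) = 0.357.

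Constant hazard, P(t) = 1 − 0.70^(t/40):
- week 40: 30.0%
- week 52: 1 − 0.70^1.3 = 37.1%
- week 80: 1 − 0.70² = 51.0%

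Front-loaded (Weibull shape 0.5), P(t) = 1 − exp(−0.357 × √(t/40)):
- week 40: 30.0%
- week 52: 33.4%
- week 80: 39.6%

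The probabilities below come from exact binomial enumeration of the two-sided 5% chi-square test with 48 per arm. They are the chance of a significant result favouring the short regimen; the nominal value is 2.5%.

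| Hazard | 40 vs 80 weeks | 52 vs 80 weeks |
|---|---|---|
| Constant | 30.0% vs 51.0%: 56% | 37.1% vs 51.0%: 28% |
| Front-loaded | 30.0% vs 39.6%: 17% | 33.4% vs 39.6%: 9% |

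**Sensitivity to the assumed risk and sample size (constant hazard).** If control risk is 30% by week 80, the investigational arm shows 1 − 0.70^(40/80) = 16.3% or 1 − 0.70^(52/80) = 20.7%. The chance is then 38% or 19% at 51 per arm, and 64% or 33% at 102 per arm. Over control risks of 10% to 60% by week 80, it runs from 14% to 93% at 102 per arm.

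**Sensitivity to timing (30% control risk, 102 per arm).** If 75% of the 80-week hazard has accrued by investigational EOT, the chance is 18%; at 90% it is 6%; at 100% the effect is gone.

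**Masking.** Under a constant hazard, equal crude proportions would conceal a hazard ratio against the short regimen of 80/52 = 1.54 or 80/40 = 2.0.

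**After the change.** With a common 40-week window and equal hazards, the expected difference is zero. The chance of a significant result favouring the short regimen returns to about 2.2–2.5% at 51 and 102 per arm.

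**The case against.** The strongest reply is that checks stop at EOT in both arms, so ascertainment follows treatment. The time gap is then largely a gap in drug exposure, and less exposure is what the short regimen offers. This stands. If toxicity mostly ends with the drugs, much of the calculated difference is a true 24-month contrast between strategies. A reader might infer that the comparison favours the short regimen through observation time alone; the documents do not support that. The calculation shows how the crude test behaves at equal weekly rates. It does not separate exposure from ascertainment.

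A reader might also infer that adverse-event collection stops at EOT. It does not, as written. Protocol 10.2 uses the trial period, and 11.2 sets no end date and requires serious events throughout. The gap is therefore mainly in non-serious grade 3+ events, and the defect is a window on which the passages disagree.

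Third, detection on treatment is more intensive in the investigational arm. Section 8.4.1 repeats ECG, neurological and colour-vision tests there, while control has them at screening only (7.1). That raises the investigational count and works against the bias described. It is a second imbalance and does not cancel the first by any known amount.

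Fourth, constant hazard may be a poor model: linezolid is reduced after two months, and in control the injectable belongs to the intensive phase. Early clustering shrinks the effect, as shown above, but the planned tables would not reveal it.

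Finally, secondary outcomes are described as exploratory and no decision rule rests on this p-value. The SAP also groups the safety set by delamanid or linezolid use. That limits the consequence, but regrouping does not equalise observation time.

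**Conclusion.** The concern holds in limited form. The documents establish a crude two-arm test over a nominal 24-month period, scheduled checks that end 28 to 64 weeks earlier in the investigational arm, and no analysis that allows for it. Such a test can favour the short regimen when event rates are equal.

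The size is unknown, because no grade 3+ rate is given. The 56% and 28% (constant hazard) and 17% and 9% (front-loaded) rest on an assumed 30% risk by week 40, 48 per arm, control observed to week 80 and no capture after EOT. Spontaneous and serious-event reporting would reduce them; a longer control course would raise them. With real exposure differences and heavier on-treatment testing also in play, neither the net direction nor the share due to ascertainment is established. This is a point to correct in the safety analysis; it does not touch the primary outcome.

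**What to change.** 1. **One collection window.** Reconcile protocol 7.1, 7.2, 8.4.2, 10.2 and 11.2. Add the adverse-drug-reaction row to the two-monthly post-EOT visits in 7.2 and 8.4.2 and to the control end-of-study visit, so that both arms are asked through month 24. State that end date in 11.2.
2. **Analyses that show exposure and time.** In SAP 3.7 and Table 23, present the 24-month proportion together with (a) grade 3+ event rates per person-month on treatment and (b) a comparison over the first 40 weeks in both arms, or time to first grade 3+ event. State that no comparative safety conclusion will be drawn from crude on-treatment proportions alone.

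The cost is one interview item at visits that already exist and some extra rows in Table 23. Treatment, sample size and the primary analysis are unchanged. The downside is small: the investigational arm's figure may become slightly less favourable as post-treatment events are recorded. The 40-week comparison leaves out half or more of the control course, so it should accompany the 24-month figure and not replace it. If data collection is complete, part 2 apart from the 24-month proportion needs no new data.
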